#### **8.1.12 Sputum Induction**

A 12-minute sputum induction using 3% hypertonic saline will be performed at visits 2, 6, 7 and 10. The procedure will be carried out according to the UCSF Airway Clinical Research Center Sputum Induction Manual of Procedures. The sputum induction procedure will only be performed at the UCSF site.

Associated risks include the following:

- Likely (>25%)
  - Salty after taste in the mouth, coughing, or a feeling of needing to swallow.
- Less Likely (<5%)
  - Sore throat, shortness of breath, wheezing, chest tightness, light-headedness, nausea, or headache.
  - Worsening of lung function.
- Rare but serious (<1%)
  - Some patients have had a severe asthma attack or a reaction to the salty water that they breathe in.

In an effort to minimize risk to participants, bronchodilator treatment will be available if sputum induction induces a worsening of asthma symptoms. The following safety procedures will be followed for the sputum induction procedure; only participants with a post-bronchodilator FEV1 of >50% predicted will undergo sputum induction, a physician will be available during the induction; study staff will calculate and record the peak flow and FEV1 value that equals both a 10% and 20% fall in lung function based upon the recorded post-bronchodilator peak flow and FEV1 values and participants will not be discharged until their FEV1 is within 10% of their post-bronchodilator FEV1.

### **8.1.13 Point of Care Urine Pregnancy Test**

A point of care urine pregnancy test will be obtained from female participants who are of childbearing potential prior to their participation in the study and routinely throughout their participation (see Appendix A).

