CONTROL PRODUCT, DOSE AND ROUTE OF ADMINISTRATION	
0.9% saline (3mL) and 2.5 mg albuterol (0.5ml)
 
Product will be administered every 8-12hours (2 times per day) for 14 days. Medication will be administered via a portable nebulizer.

DURATION OF PARTICIPATION AND DURATION OF STUDY	
Participants will be enrolled in the study up to 178 days:
 
Screening: up to 90 days
 
Treatment Period 1: 14 days
 
Washout: 60 days
 
Treatment Period 2: 14 days
 
The total duration of the study is expected to be 24 months.
 
Participant recruitment will happen on a rolling basis.

CONCOMITANT MEDICATIONS	
Prohibited:
 
 
• thiols and thiol derivatives
 
• activated charcoal
 
• inhaled insulin
 

EFFICACY EVALUATIONS	
PRIMARY ENDPOINT	The primary outcome is the % change in FEV1 from the start to the end of the treatment period (either placebo or 10% NAC).
SECONDARY ENDPOINTS	
Secondary efficacy endpoints include:
 
 
• CT mucus score
 
• FVC
 
• PEF (AM and PM)
 
• Air trapping (RV/TLC ratio)
 
• FeNO
 
• Blood eosinophils
 

OTHER EVALUATIONS	Rheological properties of sputum.
SAFETY EVALUATIONS	Incidence of adverse events
PLANNED INTERIM ANALYSES	
No interim analysis is planned
 
Serious adverse events will be monitored by the ACRC data safety monitoring committee on an ongoing basis throughout the study.

STATISTICS Primary Analysis Plan	The primary outcome is the % change in FEV1 from the start to the end of the treatment period (either placebo or 10% NAC). The first analysis will be to test the assumption of negligible carryover effects from study period 1 to period 2. We will compare the sum of the outcome values measured in the two periods for each participant across the 2 sequence groups (placebo-10% vs. 10%-placebo) using an unpaired t-test. After no or negligible carryover effect has been confirmed, we will test for the difference in treatment effects between placebo and 10% NAC using a paired t-test.

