## 8 STUDY PROCEDURES AND GUIDELINES

A Schedule of Events representing the required testing procedures to be performed for the duration of the study is diagrammed in Appendix A.

Prior to conducting any study-related activities, written informed consent and the Health Insurance Portability and Accountability Act (HIPAA) authorization must be signed and dated by the participant.

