### **8.1.14 CT Imaging of the Thorax**

A single inspiratory low dose CT scan of the thorax using a model based iterative reconstruction (MBIR) approach will be taken at visits 3, 6, 7, and 10.

The risks associated with CT scanning are that of the additional amount of radiation exposure. At the UCSF, the additional amount of radiation that each participant will receive as a result of participating in this study will be approximately 5 mSv, which is slightly greater than the yearly natural background of radiation in the US, which is 3mSv. This amount of radiation may involve a low risk of cancer. A participant should not participate in this study if she is pregnant or breastfeeding.

Additional risks are associated with the uncovering abnormal findings. There is a risk of possible detection of an abnormality in the lung which, after testing or treatment, is found not to be disease-causing. This includes possible misdiagnosis of lung cancer. Such findings may result in unnecessary anxiety for the participant, and increase his or her chance that an outpatient physician may believe that the abnormality is lung cancer and order further testing. This testing could include additional CT scans with additional radiation exposure, other types of scans to determine if the abnormalities are rapidly growing, a needle biopsy (taking a sample of the abnormality with a needle) or a lung biopsy which requires surgery. Whether these additional studies would be performed would be a decision that the participant would make with his/her regular physician.

In an effort to minimize risk to participants, scans will be read by radiologists that have expertise in interpreting findings of chest CTs. If there are any abnormalities, other than those that are usually found in asthmatic patients, observed by the clinical center radiologists, these will be reported to the principal investigator, who will in turn communicate these findings to the participant. The most likely abnormal result will be the identification of a spot on the lung that might be cancer.

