### 9.4 Visit 3 (Day 0)

1. Review and record changes to concomitant medications.
2. Perform and record vital signs.

3. Perform and record oximetry.
4. Perform and record urine pregnancy test.
5. Perform and record fractional exhaled nitric oxide (FeNO) measurement.
6. Perform and record spirometry.
7. Perform and record post-bronchodilator spirometry.
8. Obtain a CT scan of the thorax.
9. Collect blood for clinical laboratory tests.
10. Schedule participant for Visit 4 within 7 days.

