#### Appendix A. Schedule of Study Visits (UCSF)

Visit	1	2a	2b*	3	4	5	6 	7	8	9	10
Time Commitment (hours)**	2	2	3	2	8	2	4	4	8	2	4
Consent and eligibility	x										
Questionnaires	x				x	x	x	x	x	x	x
Physical Exam	x				x 	x 	x 		x 	x 	x 
Vital signs & oximetry	x	x	x	x	x	x	x	x	x	x	x
FENO					x	x	x		x	x	x
Spirometry	x	x	x	x	x	x	x	x	x	x	x

Post-bronchodilator reversibility		x		x	x	x	x	x	x	x	x
Methacholine challenge			x								
Urine pregnancy test	x	x	x		x	x			x	x	
Sputum induction		x	x				x	x			x
Blood sample					x 		x	x			x
Plethysmography					x		x		x		x
CT thorax				x			x	x			x
Nebulizer & diary card education & teach-back					x				x		
Medication administration					x	x			x	x	
Randomization					x						

\* Participation in visit 2b is dependent on post-bronchodilator reversibility test results obtained at visit 2a.

The visit 2 sputum induction will only be obtained at visit 2a or 2b.

\*\*Duration of visit is an estimation

1. Blood sample to include DNA, plasma, serum and CBC with 5-part differential
2. Abbreviated physical exam.

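### Section 9 lists a pregnancy test before the CT at Visits 3, 6, 7 and 10, but Appendices A and B leave the test blank at exactly those visits, and no clause says which prevails

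*Combined protocol and SAP*

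**What the plan says.** Section 8.1.13 is the only section devoted to the pregnancy test. It applies to women who could become pregnant, before they take part and then "routinely throughout their participation (see Appendix A"). It names no visits itself. Section 8 opens by giving that appendix the same status: "A Schedule of Events representing the required testing procedures to be performed for the duration of the study is diagrammed in Appendix A".

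Section 8.1.14 states that CT scans "will be taken at visits 3, 6, 7, and 10", and adds that pregnant or breastfeeding women should not be in the study.

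The visit lists in Section 9 give the instruction "Perform and record urine pregnancy test" at Visit 3, and the same instruction at Visits 6, 7 and 10. In each list it comes before the scan.

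The row "Urine pregnancy test" in Appendix A (UCSF) is marked at Visits 1, 2a, 2b, 4, 5, 8 and 9. The corresponding row in Appendix B (UC Davis) is the same. Both appendices mark CT at Visits 3, 6, 7 and 10.

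**The concern.** Two operative parts of the protocol give different schedules for one safety test, and they differ at every visit that involves radiation. The part to which the test's own section points is the one without the test.

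The grid does not look like a slip to someone using it. After screening, its pregnancy tests fall at Visits 4, 5, 8 and 9, the same visits as its medication-administration row. It reads as a coherent plan to test when drug is given and not when a scan is done.

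Two things are at stake: a CT in a participant whose pregnancy status was not checked that day, and different practice at the two sites. Visit 3 deserves separate mention. Section 4.1 describes its scan as the screening CT and it precedes randomization at Visit 4, so it also reaches people who then fail the mucus-score criterion.

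**Working it through.** **Inputs.** Visit days are the nominal days in the Section 9 headings: Visit 3 = 0, Visit 4 = 7, Visit 5 = 14, Visit 6 = 21, Visit 7 = 77, Visit 8 = 84, Visit 9 = 91, Visit 10 = 98. Test and scan positions come from the numbered lists in 9.4, 9.8, 9.9 and 9.13. Grid marks come from the pregnancy-test and CT rows of Appendices A and B.

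**Step 1: are the blanks real?** Tables read from PDF can lose their alignment, so the same column mapping was tested on rows whose visits the text states elsewhere. Plethysmography falls at 4, 6, 8 and 10, as in 8.1.15. CT falls at 3, 6, 7 and 10, as in 8.1.14. Randomization falls at Visit 4, as in 9.5. In Appendix A, sputum induction falls at 2a/2b, 6, 7 and 10, as in 8.1.12. The mapping is sound, and two separate site tables show the same blanks.

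**Step 2: compare the sources.** Grid age of the last test = day of scan minus day of the latest visit marked for a test in the appendix.

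| Scan visit (day) | Section 9: test item, CT item | Appendices A and B: test | Last grid test before scan | Age under grid | Age under Section 9 |
|---|---|---|---|---|---|
| 3 (0) | 4, 8 | blank | Visit 2a or 2b | not fixed | same day |
| 6 (21) | 4, 9 | blank | Visit 5 (14) | 21 − 14 = 7 days | same day |
| 7 (77) | 4, 8 | blank | Visit 5 (14) | 77 − 14 = 63 days | same day |
| 10 (98) | 4, 9 | blank | Visit 9 (91) | 98 − 91 = 7 days | same day |

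The visits where the grid leaves the test blank and the visits where it marks a CT are the same set: 3, 6, 7 and 10.

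**Step 3: the Visit 7 gap.** The 63 days are the last week of the first treatment period (21 − 14 = 7) plus the 8-week interval to Visit 7 (77 − 21 = 56). The next grid test is at Visit 8, which is 84 − 77 = 7 days after the scan.

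**Step 4: which source governs?** Sections 8 and 8.1.13 point to Appendix A. That is a pointer, not a rule of precedence, and no such rule appears elsewhere. Section 8.1.13 does not cite Appendix B, the UC Davis grid.

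**The case against.** The strongest reply is that this is an omission in a table, not two opposing orders. A blank cell does not forbid a test, Section 9 is the step-by-step instruction, and a site that complies with the whole protocol tests before every scan. Other safeguards also exist. Section 6.3 excludes women who are pregnant or unwilling to use birth control, 8.1.14 repeats that pregnant women should not take part, and 11.1 lists a positive test as a reason to stop treatment. Section 9.14 places the test (item 6) before the CT (item 12) at early withdrawal.

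Most of this stands, and it limits the point to a reconciliation. It does not remove the point, because staff who use the grid are following an explicit pointer and none of the other safeguards establishes status on the day of a scan.

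It is also fair that the grids differ from Section 9 elsewhere. FeNO is at Visits 3 and 7 but not 5 and 9 in Section 9, and the reverse in the grids. Baseline blood is at Visit 3 in 8.2.1 and 9.4 but at Visit 4 in the grids. This supports checking the appendices as a whole; it does not excuse the safety row.

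Three stronger readings are tempting, and the documents do not support them.

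- A reader might infer that the protocol fails to require a test before CT. It does require one, in Section 9.
- A reader might take the screening window of up to 90 days as the size of the Visit 3 gap. The documents do not agree on a limit. The synopsis says "Participants will be enrolled in the study up to 178 days"; with Visit 10 on Day 98 that leaves 178 − 98 = 80 days before Visit 3. Section 4.1 gives 16 weeks of participation, or 112 days, which leaves 112 − 98 = 14. All that can be said is that the interval is not fixed.
- A reader might use the radiation figure of about 5 mSv in 8.1.14 to size the harm. That is a participant's whole-study dose at UCSF and does not measure exposure of a pregnancy.

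**Conclusion.** The schedule is wrong as written and should be corrected. Section 9 and the appendices conflict on the pregnancy test at all four CT visits, and the protocol directs staff to the version without it. If the grid is followed, no scan has a same-day test; the last test is 7, 63 and 7 days old at Visits 6, 7 and 10, and of no fixed age at Visit 3. If Section 9 is followed, every scan has a same-day test.

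The day counts assume nominal visit days and no unscheduled test. The point concerns only women who could become pregnant; the protocol plans 36 participants aged 18 to 80 and does not say how many that would be. The documents do not show which source the sites used, so nothing here implies that any scan was done without a test. Efficacy, the analysis and the sample size are not affected.

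**What to change.** Mark the urine pregnancy test at Visits 3, 6, 7 and 10 in Appendices A and B so that both match Section 9. In 8.1.13, replace the reference to Appendix A alone with a reference to Section 9 and both appendices.

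The cost is four cells in each of two tables (4 × 2 = 8) and one cross-reference. No visit is added, and no test beyond those Section 9 already lists.

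Optionally, and separately, add one sentence to 8.1.13 saying that the result must be negative before each CT in women who could become pregnant. This would be a new rule, although the step order in Section 9 and the statement in 8.1.14 already lean that way. The reconciliation does not depend on it.

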### **8.1.14 CT Imaging of the Thorax**

A single inspiratory low dose CT scan of the thorax using a model based iterative reconstruction (MBIR) approach will be taken at visits 3, 6, 7, and 10.

The risks associated with CT scanning are that of the additional amount of radiation exposure. At the UCSF, the additional amount of radiation that each participant will receive as a result of participating in this study will be approximately 5 mSv, which is slightly greater than the yearly natural background of radiation in the US, which is 3mSv. This amount of radiation may involve a low risk of cancer. A participant should not participate in this study if she is pregnant or breastfeeding.

Additional risks are associated with the uncovering abnormal findings. There is a risk of possible detection of an abnormality in the lung which, after testing or treatment, is found not to be disease-causing. This includes possible misdiagnosis of lung cancer. Such findings may result in unnecessary anxiety for the participant, and increase his or her chance that an outpatient physician may believe that the abnormality is lung cancer and order further testing. This testing could include additional CT scans with additional radiation exposure, other types of scans to determine if the abnormalities are rapidly growing, a needle biopsy (taking a sample of the abnormality with a needle) or a lung biopsy which requires surgery. Whether these additional studies would be performed would be a decision that the participant would make with his/her regular physician.

In an effort to minimize risk to participants, scans will be read by radiologists that have expertise in interpreting findings of chest CTs. If there are any abnormalities, other than those that are usually found in asthmatic patients, observed by the clinical center radiologists, these will be reported to the principal investigator, who will in turn communicate these findings to the participant. The most likely abnormal result will be the identification of a spot on the lung that might be cancer.

### **8.1.15 Body Plethysmography**

Body plethysmography will be done to determine functional residual capacity (FRC), residual volume (RV), total lung capacity (TLC), and slow vital capacity (SVC) at Visit 4, 6, 8 and 10. Plethysmography will be done with bronchodilation. If bronchodilation procedures are done, participants will follow the medication hold times as described in Section 9.1.2. In an effort to minimize risk to participants, patients with severe claustrophobia, inability to sit upright in a chamber, inability to perform the panting maneuver, inability to perform maximal inspiratory and expiratory efforts, and known perforated tympanic membrane without a snug-fitting earplug will be excluded from participation in the study.

### 8.1.16 Measurement of Fractional Exhaled Nitric Oxide

Fractional exhaled nitric oxide measurement test will be performed at Visits 3-10. Subjects will inhale a full breath of air and then exhale it slowly through a mouthpiece while a device measures the concentration of nitric oxide in the air exhaled. Nitric oxide is a gas normally present in the air exhaled from the lungs.

### 8.1.17 Adverse Events

Information regarding occurrence of adverse events will be captured throughout the study. Duration (start and stop dates and times), severity/grade, outcome, treatment and relation to study drug will be recorded on the case report form (CRF).

## 8.2 Clinical Laboratory Measurements

### 8.2.1 Hematology

UCSF: Up to 100 mL (about 7 tablespoons) of blood will be obtained by standard venipuncture, for the collection of DNA, plasma, serum, and complete blood count with differential (CBC-D). Blood collection for DNA will be obtained at visit 3 and blood collection for plasma, serum and CBC-D will be collected at visits 3, 6, 7 and 10.

UC Davis: Up to 15 mL (about 1 tablespoon) of blood will be obtained by standard venipuncture for the collection of complete blood count with differential (CBC-D). Blood collection for CBC-D will be collected at visits 3, 6, 7, and 10.

Risks associated with hematology include the following risks associated with venipuncture:

- Lightheadedness or nausea while having blood drawn
- Bruising at the site where the needle enters the skin and a remote risk of infection

In an effort to minimize risk to participants, aseptic technique will be used and pressure applied to site to prevent infection/bruising. Participants who have previously identified that they experience lightheadedness during blood draws will have blood drawn while lying supine on an exam room table.

## 8.3 Research Laboratory Measurements

Induced sputum will be collected at visits 2, 6, 7, and 10.

### 8.3.1 Sputum Cell Count and Differential

Sputum for determination of total and differential cell counts will be collected at visits 2, 6, 7 and 10. Specimens will be collected and processed according to the UCSF Airway Clinical Research Center Sputum Induction Manual of Procedures (Appendix C).

### 8.3.2 Sputum Cytokine Gene Expression Measurements

Sputum for determination of RNA gene expression of a number of airway-specific genes will be collected at visits 2. Specimens will be collected and processed according to the UCSF Airway Clinical Research Center Sputum Induction Manual of Procedures.

### 8.3.3 Sputum Rheology

Sputum for the determination of rheological properties will be collected at visits 2, 6, 7, and 10. The rheological measurements may be made using a portion of the sample collected at this time. Sputum will only be collected for rheology at the UCSF site.

## 9 EVALUATIONS BY VISIT

### 9.1 Visit 1

1. Review the study with the participant and obtain written informed consent and HIPAA authorization.
2. Assign the participant a unique screening number.
3. Record demographics data.
4. Record medical history, including history of asthma, diagnosis date, and asthma-related healthcare utilization & exacerbation frequency.
5. Record concomitant medications.
6. Perform a complete physical examination.
7. Perform and record vital signs.
8. Perform and record oximetry.
9. Perform and record urine pregnancy test.
10. Perform and record spirometry.
11. Schedule participant for Visit 2.

### 9.2 Visit 2a

1. Review and record changes to concomitant medications.
2. Perform and record vital signs.
3. Perform and record oximetry.
4. Perform and record urine pregnancy test.
5. Perform and record spirometry.
6. Perform maximum reversibility and record post-bronchodilator spirometry.
7. If FEV1 bronchodilator reversibility of  $\geq 12\%$  collect induced sputum and schedule for Visit 3.
8. If FEV1 bronchodilator reversibility of  $\leq 12\%$  schedule participant for Visit 2b.

### 9.3 Visit 2b \*\*Optional

1. Perform and record vital signs.
2. Perform and record oximetry.
3. Perform and record urine pregnancy test.
4. Perform and record spirometry.
5. Perform methacholine challenge testing.
6. Collect induced sputum.
7. Schedule participant for Visit 3.

### 9.4 Visit 3 (Day 0)

1. Review and record changes to concomitant medications.
2. Perform and record vital signs.

3. Perform and record oximetry.
4. Perform and record urine pregnancy test.
5. Perform and record fractional exhaled nitric oxide (FeNO) measurement.
6. Perform and record spirometry.
7. Perform and record post-bronchodilator spirometry.
8. Obtain a CT scan of the thorax.
9. Collect blood for clinical laboratory tests.
10. Schedule participant for Visit 4 within 7 days.

#### **9.5 Visit 4 (Day 7)**

1. Review and record changes to concomitant medications.
2. Perform and record vital signs.
3. Perform and record oximetry.
4. Perform and record urine pregnancy test
5. Perform and record fractional exhaled nitric oxide (FeNO) measurement.
6. Perform and record spirometry.
7. Perform and record post-bronchodilator reversibility.
8. Perform and record plethysmography with bronchodilation.
9. Randomize
10. Provide education on use of personal nebulizer and administration of study medication.
11. Administer first two treatments of study drug treatment, spaced 4-6 hours. FEV1 measurements should be taken before and after each treatment.
12. Dispense study drug and initiate study diary if subject's post-treatment FEV1 is greater than 80% of pre-treatment FEV1.
13. Schedule participant for phone follow-up in 3-5 days and visit 5 in 7 days.

#### **9.6 Phone follow-up (Day 9, 10, or 11)**

1. Administer questionnaire to monitor for treatment related side effects.

#### **9.7 Visit 5 (Day 14)**

1. Review and record any adverse experiences and/or review participant diary for adverse experiences and exclusionary medication use
2. Review and record concomitant medications.
3. Perform abbreviated physical examination.
4. Perform and record vital signs.
5. Perform and record oximetry.
6. Perform and record urine pregnancy test
7. Perform and record spirometry.
8. Perform and record post-bronchodilator spirometry.
9. Collect any unused study drug.
10. Review diary card.
11. If subject's adherence is greater than 70%, dispense 7 days of study drug.
12. Schedule participant for Visit 6 in 7 days.

